11.2 Safety Evaluation

The following analyses will be performed; however, no formal inferential statistics will be done on safety assessments.

Descriptive statistics will be presented by scheduled study visit for quantitative safety data and frequency counts will be compiled for classification of qualitative safety data. Summaries of local tolerability will be presented by scheduled study visit.

11.2.1 Adverse Events

All treatment-emergent AEs occurring during the study will be recorded and classified on the basis of MedDRA terminology for the safety population. Treatment-emergent AEs are those AEs with an onset on or after the date of study treatment. All treatment-emergent AEs will be

summarized by scheduled study visit, the number of subjects reporting treatment-emergent AEs, system organ class, preferred term, severity, relationship, and seriousness.

Serious adverse events (SAEs) will be listed by subject. SAEs will be summarized by severity and relationship to study treatment. Each subject will be counted only once within a system organ class or a preferred term using the event with the greatest relationship and greatest severity.

All information pertaining to AEs noted during the study will be listed by subject, detailing the verbatim description given by the Investigator, preferred term, system organ class, start date, stop date, severity, action taken regarding study drug, corrective treatment, outcome, and drug relatedness. The event onset will also be shown relative (in number of days) to date of first application. In addition, a list of subjects who prematurely discontinue from the study due to adverse events will also be provided.

A subject-by-subject treatment-emergent AE (TEAE) data listing, including verbatim term, preferred term, treatment, severity, and relationship to study drug, will be provided.

Medical history will be listed by subject. Physical examinations and 12-lead ECGs will be listed by subject.

11.2.2 Medical History and Physical Examinations

Medical history for all subjects will be presented in a by-subject listing.

Physical examination findings for all subjects will be presented in a by-subject listing. Changes in physical examinations will be described in the text of the final report.

11.2.3 Clinical Laboratory Results and Vital Signs/Weight Measurements

Vital signs will be tabulated by scheduled study visit.

Routine blood chemistries and urinalysis will be obtained throughout the study and the results summarized by parameter and at scheduled study visits.

All clinical laboratory results and vital signs measurements and their change from baseline will be summarized along with timepoint of collection.

A shift table describing out-of-normal range shifts will be provided for clinical laboratory results.

A shift table will identify subjects who gain or lose >5% body weight over the course of the study.

11.2.4 ECG:

ECGs will be tabulated by scheduled study visit.

11.2.5 Local Tolerance Assessments:

For the Investigator's assessment the numeric application site reaction scores will be summarized individually by using number and percentage of subjects by visit.

11.2.6 PHQ-8

Data will be analyzed by a shift in state of severity using the following scoring system:

- None – Minimal depression (0 to 4)
- Mild depression (5 to 9)
- Moderate depression (10 to 14)
- Moderately severe depression (15 to 19)
- Severe depression (20 to 24)

11.2.7 C-SSRS

The C-SSRS will be analyzed per the Columbia–Suicide Severity Rating Scale Scoring and Data Analysis Guide.

11.2.8 Prior and Concomitant Medications

Prior and concomitant medication information for all subjects will be presented in a by-subject listing. Summary tables will be presented by World Health Organization-Anatomical Therapeutic Chemical Classification System (WHO-ATC) therapeutic category and product.

11.3 Efficacy Evaluation

This study is not intended to assess efficacy, but rather the IGA, I-IGA and mPASI are included to determine the need for treatment and subsequent re-treatment after treatment course in Study ARQ-151-201 or Study ARQ-151-202. Certain efficacy data and endpoints will, however, be summarized.

Descriptive statistics will be used to summarize the assessment of efficacy. IGA scores will be summarized at Baseline Visit of Study ARQ-151-201 and every scheduled visit through end of the study (Day 1 and Weeks 4, 12, 24, 36, and 52). The efficacy variable in this study is success in Investigator Global Assessment (IGA) of disease severity, defined as an IGA of 'Clear' or 'Almost Clear'. The number and percentage of patients who achieve treatment success at the scheduled study visits will be tabulated. The proportion of successes for the secondary variables of I-IGA and 75% reduction in mPASI will be tabulated in a similar manner.

The number of treatment free days until the first retreatment (relapse) will be calculated and analyzed. For rollover subjects previously treated with Vehicle Cream, the number of treatment free days will be the number of days between the end of the initial treatment in study ARQ-151-202 and the start of the next treatment in study ARQ-151-202 if one should be needed or the end of the subject's participation in study ARQ-151-202. For rollover subjects previously treated

with ARQ-151 cream 0.3% or ARQ-151 cream 0.15%, the number of treatment free days will be the number of days between the last treatment that began in Study ARQ-151-201 and the start of the next treatment in study ARQ-151-202 if one should be needed or the end of the subject's participation in the study ARQ-151-202. There may be additional analyses comparing subjects that were previously treated with ARQ-151 cream 0.3% and ARQ-151 cream 0.15% in the ARQ-151-201 study.

Descriptive statistics for retreatment rates will be presented. The time (number of days) to relapse will be analyzed using the Kaplan–Meier method. The median time to relapse will be calculated in addition to other appropriate descriptive statistics. Patients who discontinue study ARQ-151-202 without relapse will be considered censored in the Kaplan–Meier analysis.

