8.2.2 Secondary Endpoints

The secondary endpoints are related to efficacy and will include:

- Proportion (%) of subjects achieving an Investigator Global Assessment (IGA) of clear or almost clear, as observed at Week 12 and subsequent scheduled visits.
- In subjects who achieve 'clear' scores for IGA, I-IGA (if applicable **and** mPASI (Modified Psoriasis Area Severity Index) and stop treatment to all lesions, time to re-starting study drug (duration of response).
- Proportion (%) of applicable subjects with intertriginous area involvement, 'I-IGA' score of 'clear' or 'almost clear' at week 12 and subsequent visits
- Proportion (%) of subjects achieving a 75% reduction from Baseline of Modified Psoriasis Area Severity Index-75 (mPASI-75) at weeks 12, 24, 36 and 52 as compared to Baseline.

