10.5 Unscheduled Visit

Subjects that clear between scheduled visits should return for an unscheduled visit for the investigator to confirm IGA, I-IGA (if applicable) and mPASI are clear and subject may stop application of study drug. Unscheduled visits may be necessary for the purpose of measuring time to restarting study drug for those subjects that stopped application of study medication due to resolution of psoriasis plaques. Subjects will call the site when psoriasis returns prior to restarting application of study drug. Unscheduled visits also may be necessary to repeat testing following abnormal laboratory results, for follow-up of AEs, or for any other reason, as warranted in the judgement of the Investigator.

The following information will be collected for all subjects:

- Concomitant medications/procedures
- AEs

The following information will be collected for those subjects that had stopped study medication but are experiencing a reoccurrence of psoriasis plaques:

- Time between stopping study medication and restarting application
- Investigator's Global Assessment (IGA) of psoriasis severity
- Body Surface Area (BSA) of psoriasis involvement (not palms, soles, or scalp)

An updated Body Diagram of psoriasis involvement should be provided to the subject.

The rules for how to tally IGA or other proportions of categorical responses will be described in the Statistical Analysis Plan.

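### Subjects who leave or finish with returned psoriasis but no restart of drug are censored as relapse-free, so the Kaplan-Meier median time to relapse is biased upward

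*Protocol*

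**What the plan says.** The protocol's Secondary Endpoints (8.2.2) describe, for subjects who clear and "stop treatment to all lesions, time to re-starting study drug (duration of response"). The synopsis uses the same idea.

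Section 11.3 gives the analysis. The event is the first retreatment, with relapse in parentheses as its synonym: "The number of treatment free days until the first retreatment (relapse) will be calculated and analyzed". No other definition of relapse appears. The estimator and summary follow: "The time (number of days) to relapse will be analyzed using the Kaplan–Meier method", and "The median time to relapse will be calculated in addition to other appropriate descriptive statistics". The censoring rule is: "Patients who discontinue study ARQ-151-202 without relapse will be considered censored in the Kaplan–Meier analysis". For subjects who need no further treatment, the day count runs to the end of their participation.

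The procedures treat return of disease as a separate, earlier step. Section 10.5 says: "Subjects will call the site when psoriasis returns prior to restarting application of study drug". Sections 10.1.9 and 10.8 say the same. For subjects with recurrence, section 10.5 lists the stop-to-restart interval, IGA and BSA, but not the date on which psoriasis returned.

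**The concern.** Because relapse means retreatment, 'without relapse' in the censoring rule means 'without having restarted drug'. Three routes in the protocol lead from returned psoriasis to censoring:

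- **Withdrawal by choice** after psoriasis returns (9.6.3, item 4).
- **Removal for needing a prohibited medication** (9.6.3, item 7). Table 1 prohibits other systemic and topical psoriasis therapies, so a relapsed subject who needs one can be removed.
- **Reaching Week 52 with recurrence.** The Schedule of Visits shows no dispensing at Week 52, so a recurrence first seen there does not normally become a retreatment.

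Kaplan-Meier assumes that a censored subject has the same future risk as those still followed. Here the censored subject has already relapsed. At stake is the study's one time-to-event estimate of how long response lasts, published under the names time to relapse and duration of response.

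**Working it through.** **Inputs.** The event, censoring rule and estimator come from section 11.3, and the order of return, call and restart from section 10.5. The protocol states no median, leaving rate or delay for this endpoint, so there is no figure to reproduce. The true median m and the share q of relapsers who leave at return without restarting are assumptions, shown over a range.

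**Step 1: direction.** Let psoriasis return with cumulative hazard H(t), so that true relapse-free survival is S(t) = exp(−H(t)). If a constant share q of returns is recorded as censoring, only (1−q) of the hazard is counted, and Kaplan-Meier estimates exp(−(1−q)H(t)) = S(t)^(1−q). This is never below S(t), whatever the shape of S. At the true median, where S = 0.5, the estimated curve reads 0.5^0.9 = 0.536 for q = 10% and 0.5^0.8 = 0.574 for q = 20%.

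**Step 2: size with exponential return times.** The true hazard is ln 2 / m and the counted hazard is (1−q) ln 2 / m, so the estimated median is m/(1−q).

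| True median (days) | q = 5% | q = 10% | q = 20% | q = 30% |
|---|---|---|---|---|
| 60 | 63.2 | 66.7 | 75.0 | 85.7 |
| 90 | 94.7 | 100.0 | 112.5 | 128.6 |
| 120 | 126.3 | 133.3 | 150.0 | 171.4 |
| Inflation | +5% | +11% | +25% | +43% |

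For example, 90/(1 − 0.10) = 100.0 days, which is 100/90 − 1 = +11%. At q = 0 the inflation is zero.

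**Step 3: simulation.** This used 20,000 subjects per scenario, off-drug periods starting uniformly between days 28 and 252 of 364, no delay from return to restart, and a true median of 90 days. For q = 5, 10, 20 and 30%, the plan's rule gave medians of 96, 100, 112 and 129 days. Counting return as the event gave 92, 89, 89 and 90 in the same data. The closed form holds up under the study's limited follow-up.

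**Step 4: can the median move down?** In 3,000 simulated samples of 30 subjects, with 20% leaving and random delays, the plan's median was never below the return-based median. One apparent exception was a rounding tie at a survival estimate of exactly 0.5 and disappeared once a tolerance was set.

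**Limit of the formula.** It describes subjects who leave when psoriasis returns. Recurrence first seen at Week 52 acts on the right-hand end of the curve and reaches the median only if the median is long.

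**The case against.** The strongest reply is that the endpoint is openly defined as time to restarting drug. Treatment-free time is a legitimate quantity, and for it the interval between return and restart is not an error. That stands. A reader might infer that the whole delay is bias: a 7-day delay with q = 10% and a true median of 90 days gives about 108 days in simulation, against 100 without delay. The documents do not support that reading. They require only a call before restart, say that an unscheduled visit may be needed, and give no delay.

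Other stronger readings also fail:

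- **A subject with visible disease who stays off drug and counts as responding.** Section 9.8.2 tells subjects to keep treating active lesions and new plaques. The synopsis is softer on resuming, but this is largely off the described pathway.
- **The only durability result.** Section 11.3 also reports IGA success at every scheduled visit, I-IGA, mPASI-75 and retreatment rates.
- **Response should end as soon as any scale is no longer clear.** This is debatable. Section 11.3 defines IGA success as clear or almost clear, clinic visits after Week 12 are 12 to 16 weeks apart, and section 10.5 does not list I-IGA or mPASI among the data for recurrence.

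It can also be said that censoring detail belongs in the SAP, which is not shown, and that section 11.1 describes itself as a summary. But the protocol itself fixes both the event and the censoring rule; section 10.5 leaves to the SAP only how IGA and other categorical responses are tallied.

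Finally, much of the needed information exists. Early-termination visits repeat the final-visit assessments (10.4), a psoriasis flare is an adverse event (10.1.8), and its onset date is recorded (10.6.5). This makes repair easy, but nothing in 11.3 links these data to the endpoint.

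**Conclusion.** The point holds for the censoring rule. As written, subjects with returned psoriasis and no restart are counted as relapse-free when they leave or finish. A median labelled time to relapse or duration of response can then only be too long.

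The factor 1/(1−q) assumes exponential return times, departure at the time of return, and the same leaving share throughout. The size cannot be determined from the protocol, and is nil if no relapser leaves or finishes without restarting. Even if the result is read strictly as time to restart, censoring subjects who leave with active disease remains informative, and the relapse label is wrong for them.

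The correction is worth making, but its reach is limited. The protocol says the study is not intended to assess efficacy, and no test or decision rule depends on this median.

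**What to change.** In section 11.3, for the time-to-relapse analysis:

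1. Count as the event the earliest of restart of study drug, start of another psoriasis therapy, or discontinuation or study end with documented returned psoriasis. Date the last of these by the subject's call, the flare adverse-event onset or the visit, and state the order of precedence and what counts as documented return.
2. Censor only subjects without documented return at their last assessment.
3. Record the date of return at the call the protocol already requires.
4. Report stop-to-restart time separately, labelled treatment-free time, and align the label in 8.2.2 and the synopsis.

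The cost is one extra recorded date, a wording amendment, and a somewhat shorter stated duration. No treatment rule or visit changes.

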12 STUDY ADMINISTRATION

12.1 Ethics

12.1.1 Ethics Review Board

Before enrollment of patients into the study, the current protocol and ICF will be reviewed and approved by an appropriate IRB or IEC, as required by FDA (21 CFR § 56), Health Canada, and ICH GCP regulations. A letter documenting the IRB or IEC approval must be received by the Sponsor before the initiation of the study at a clinical site. Amendments to the protocol will be subject to the same requirements as the original protocol.

The Investigator, Sponsor, or designee will submit a progress report at least once yearly to the IRB or IEC. However, the frequency of these reports will depend on IRB or IEC requirements. As soon as possible after completion or termination of the study, the Investigator will submit a final report to the IRB or IEC per the IRB or IEC requirements, and in compliance with FDA and Health Canada regulations and ICH GCP guidelines.

The Investigator, the Sponsor, or designee shall promptly notify the IRB or IEC of any SAEs, SUSARs, or any other information that may affect the safe use of the study drug(s) during the study, per the IRB or IEC local requirements, and in compliance with FDA and Health Canada regulations and ICH GCP guidelines.

12.1.2 Ethical Conduct of the Study

This research will be carried out in accordance with the protocol, the principles of the Tri-Council Policy Statement (TCPS), the ethical principles set forth in the Declaration of Helsinki, and the ICH harmonized tripartite guideline regarding GCP (E6 Consolidated Guidance, April 1996).

12.1.3 Subject Information and Consent

The purpose of the study, the procedures to be carried out and the potential hazards will be described to the subjects in non-technical terms. Subjects will be required to read, sign and date an ICF summarizing the discussion prior to screening and will be assured that they may withdraw from the study at any time without jeopardizing their medical care.

Subjects will be given a signed copy of their ICF.

12.2 Study Monitoring

Prior to the initiation of the clinical investigation, Sponsor representatives or designees will visit the clinical site where the investigation is to be conducted. Sponsor representatives shall ensure that the Investigator understands the investigational status of the investigational product, all requirements of the investigation to be undertaken, and all of his/her responsibilities as an Investigator. Sponsor representatives will also visit the clinical site at appropriate intervals as required to ensure compliance with the protocol and to verify the accuracy and completeness of data reported on the CRFs. The Study Director or designees shall be available for consultation with the Investigator and serve as liaisons between the clinical site and the Sponsor.

The Sponsor or authorized designees may inspect all documents and records required to be maintained by the Investigator, including but not limited to medical records (office, clinic, or hospital) and investigational product dispensation logs for the subjects in this clinical investigation. The Investigator must permit access to such records. The Investigator must obtain, as part of informed consent, permission for an authorized representative of the Sponsor, or regulatory authorities, to review, in confidence, any records identifying subjects.

12.3 Data Quality Assurance

In order to ensure the collection of accurate, consistent, complete, and reliable data during this clinical investigation, Sponsor representatives or designees may conduct audits of participating sites at appropriate intervals throughout the study. The results of these periodic site audits may be subject to review by independent auditors at completion of the clinical investigation. The Clinical Study Report will be audited by the QST's Research's Quality Assurance (QA) department and the QA audit certificate will be included in the study report.

All clinical data will undergo a 100% quality control check prior to clinical database lock. Edit checks are then performed for appropriate databases as a validation routine using SAS® to check for missing data, data inconsistencies, data ranges etc. Corrections are made prior to database lock.

12.4 Data Handling and Record Keeping

During the clinical study, the Investigator will maintain adequate records, including medical records, records detailing the progress of the study for each subject, laboratory reports, signed informed consent forms, investigational product disposition records, correspondence with the ERB/IRB and Study Monitor/Sponsor, AE reports, and information regarding subject discontinuation and completion of the clinical investigation.

All required study data will be recorded on eCRFs. Any change of data will be recorded on the audit trail and a reason for the change will be entered.

The principal investigator must retain all documentation relating to the study for a period of at least 2 years after the last marketing application approval or, if not approved, 2 years following the discontinuance of the test article for investigation. If this requirement differs from any local regulations, the local regulations will take precedence unless the local retention policy is less than 2 years.

12.5 Protocol Amendments and Deviations

No change or amendment to this protocol may be made by the investigator or Sponsor after the protocol has been agreed to and signed by all parties unless such change(s) or amendment(s) has (have) been agreed upon by the investigator and Sponsor. Any change agreed upon will be recorded in writing, and the written amendment will be signed by the investigator and Sponsor. Institutional review board approval is required prior to the implementation of an amendment, unless overriding safety reasons warrant immediate action, in which case the IRB(s) will be promptly notified.

No deviation from the protocol will be made except to protect the life or physical well-being of a subject in an emergency. Except in such emergencies, prior approval of the Sponsor, and the IRB, is required before deviations from the planned protocol. All protocol deviations that occur during the study will be documented and reported to Sponsor and to the IRB(s), if applicable, according to regulations. Further details about the documentation, evaluation, and follow-up of protocol deviations are detailed in this study's clinical monitoring plan.

No waivers to inclusion/exclusion criteria will be granted; subjects need to meet all criteria, exactly as specified, to be enrolled. Additionally, prospective deviations from the protocol or investigational plan are not permitted except to protect the life or physical well-being of a subject in an emergency. Deviations that occur unintentionally or are the result of action by the subject must be documented and reported to the IRB(s), if applicable, according to regulations. Further details about the documentation, evaluation, and follow-up of protocol deviations are detailed in this study's clinical monitoring plan.

12.6 Report Format

According to the ICH Harmonized Tripartite Guideline (Organization of the Common Technical Document for the Registration of Pharmaceuticals for Human Use M4 and the ICH M2 Expert Working Group), the final report will be written according to the ICH E3 Guideline (Structure and Content of Clinical Study Reports).

